7.1.1.7. Visit 7 (Beginning on the Morning of Day 20)

The following will be performed during Visit 7

- Admission to the CRU on Day 20
- Clinical labs, urine drug screen, breath alcohol, vital signs, C-SSRS, concomitant medications on Day 20
- Blood sample to determine plasma drug concentrations of cenobamate on Day 20 for end of Period 1 sampling
- Dosing of cenobamate per randomized treatment allocation on Day 22
- Physical exam (symptom oriented) and vital signs on Day 22

- Blood sampling to determine plasma drug concentrations of cenobamate on Day 22 to the morning of Day 25 for beginning of Period 2 sampling
- Clinical labs, vital signs, and concomitant medications on Day 25
- AE Monitoring throughout
- Discharge on the morning of Day 25; upon discharge, subjects will be issued a hypersensitivity safety card

7.1.1.8. Visit 8 (Morning of Day 27)

The following will be performed during Visit 8

- Outpatient visit
- Urine drug screen, breath alcohol, vital signs, and concomitant medications
- AE Monitoring throughout
- Blood sample to determine plasma drug concentrations of cenobamate

7.1.1.9. Visit 9 (Morning of Day 30)

The following will be performed during Visit 9

- Outpatient visit
- Urine drug screen, breath alcohol, vital signs, and concomitant medications
- AE Monitoring throughout
- Blood sample to determine plasma drug concentrations of cenobamate

7.1.1.10. Visit 10 (Morning of Day 33)

The following will be performed during Visit 10

- Outpatient visit
- Urine drug screen, breath alcohol, vital signs, and concomitant medications
- AE Monitoring throughout
- Blood sample to determine plasma drug concentrations of cenobamate

7.1.1.11. Visit 11 (Morning of Day 37)

The following will be performed during Visit 11

- Outpatient visit
- Urine drug screen, breath alcohol, vital signs, and concomitant medications
- AE Monitoring throughout
- Blood sample to determine plasma drug concentrations of cenobamate

7.1.1.12. Visit 12 (Beginning on the Morning of Day 41)

The following will be performed during Visit 12

- Admission to the CRU on Day 41
- Clinical labs, urine drug screen, breath alcohol, vital signs, C-SSRS, concomitant medications on Day 41
- Blood sample to determine plasma drug concentrations of cenobamate on Day 41 for end of Period 2 sampling
- Physical exam (symptom oriented) and vital signs on Day 43
- Dosing of cenobamate per randomized treatment allocation on Day 43
- Blood sampling to determine plasma drug concentrations of cenobamate on Day 43 to the morning of Day 46 for beginning of Period 3 sampling
- Clinical labs, vital signs, and concomitant medications on Day 46
- AE monitoring throughout
- Discharge on the morning of Day 46; upon discharge, subjects will be issued a hypersensitivity safety card

7.1.1.13. Visit 13 (Morning of Day 48)

The following will be performed during Visit 13

- Outpatient visit
- Urine drug screen, breath alcohol, vital signs, and concomitant medications
- AE Monitoring throughout
- Blood sample to determine plasma drug concentrations of cenobamate

7.1.1.14. Visit 14 (Morning of Day 51)

The following will be performed during Visit 14

- Outpatient visit
- Urine drug screen, breath alcohol, vital signs, and concomitant medications
- AE Monitoring throughout
- Blood sample to determine plasma drug concentrations of cenobamate

7.1.1.15. Visit 15 (Morning of Day 54)

The following will be performed during Visit 15

- Outpatient visit
- Urine drug screen, breath alcohol, vital signs, and concomitant medications
- AE Monitoring throughout

- Blood sample to determine plasma drug concentrations of cenobamate

7.1.1.16. Visit 16 (Morning of Day 58)

The following will be performed during Visit 16

- Outpatient visit
- Urine drug screen, breath alcohol, vital signs, and concomitant medications
- AE Monitoring throughout
- Blood sample to determine plasma drug concentrations of cenobamate

7.1.1.17. Visit 17 (Morning of Day 62)

The following will be performed during Visit 17

- Outpatient visit
- Urine drug screen, breath alcohol, vital signs, and concomitant medications
- AE Monitoring throughout
- Blood sample to determine plasma drug concentrations of cenobamate

7.1.1.18. Visit 18 Follow-Up (Day 69)

The following will be performed during Visit 18

- Final outpatient visit
- Urine pregnancy, clinical labs, physical exam (symptom oriented), vital signs C-SSRS and concomitant medications
- AE Monitoring throughout

7.2. Number of Subjects

A total of 24 (4 subjects per sequence) healthy female and male subjects, balanced by gender and race/ethnicity to the extent possible, will be included in the study.

If needed and agreed upon by SKLSI and investigator, replacement subjects will be assigned to the same treatment sequence as the subject they are replacing in order to have at least 20 subjects completing all three treatments.

7.3. Treatment Assignment

The study will contain the following treatment groups:

- **Treatment A:** 200 mg cenobamate oral tablet under fasting condition
- **Treatment B:** 200 mg cenobamate oral suspension under fasting condition
- **Treatment C:** 200 mg cenobamate oral suspension under fed condition

7.3.1. Methods for Treatment Group Assignment

After obtaining oral and written informed consent, subjects will be screened according to the inclusion and exclusion criteria (Section 8.1 and Section 8.2). Prior to dosing on Day 1, subjects will be randomized to receive one of three treatment schemes as outlined in [Table 3](#). The randomization schedule will be generated by the statistician responsible for this study using SAS® software. One copy of the randomization list will be provided to the pharmacist for preparation of the appropriate treatment. Subjects withdrawn from the study retain their randomization number, if already given. New subjects must always be allotted a new randomization number. Once assigned, randomization numbers must not be reused within the study site.

Subjects who drop-out for any reason or withdraw consent prior to dosing will be considered as screen failures. Such subjects will not receive a unique subject number. The Investigator will keep a screening log of all screen failure subjects, along with the reasons for their screen failure.

7.3.2. Allocation of Subject Numbers

Once a subject has signed the ICF, that subject will be assigned an 8-digit subject identification number (subject ID) e.g. 01001001. The first two digits is for country, the next 3 digits for site, and the last 3 digits for subject. Subject numbers will be allocated sequentially in the order in which the subjects are screened. Once assigned, subject identification numbers must not be reused. The subject number will ensure identification throughout the study.

Subjects withdrawn from the study will retain their subject identification numbers. Any replacement subject will receive the subject number from the subject they are replacing + 100, e.g., replacement for 01001003 would have the subject identification number 01001103.

Subjects who fail screening will be allowed to re-screen only once. The re-screened subject will be assigned a new subject number, and the linking information for these two subject numbers will be recorded in CRF.

7.4. Dose Adjustment Criteria

The dose will not be adjusted in this study.

7.4.1. Safety Criteria for Adjustment or Stopping Doses

The dose of this study will not be adjusted. However, the Investigator may withdraw a subject at any time if it is determined that continuing the study would result in a significant safety risk to the subject.

Subjects will be discontinued from the clinical study for any of the following reasons:

- Females who are pregnant according to a positive pregnancy test,
- Positive screening of alcohol and/or drugs of abuse,
- If following the first dose, a subject develops any rash related to the study drug.

Furthermore, participation in the clinical study could be discontinued by the Investigator in charge of the study or by SKLSI for any of the following reasons:

- Clinically significant abnormality on vital signs, clinical laboratory, or physical examination assessments, as assessed by the investigator or designee,
- Rash or manifestation of hypersensitivity reaction such as lymphadenopathy, fever, or facial swelling related to the study drugs,
- Noncompliance with the protocol requirements (e.g., blood collection deviations which may impact the PK profile),
- The subject is uncooperative during the study,
- Occurrence of intolerable adverse event (AE),
- Lost to follow-up,
- Unanticipated event which could result in an inadequately characterized PK profile, such as missed blood draws, AE, or need to use concomitant medications.

If a subject prematurely discontinues, or is discontinued from the study, the primary reason for the discontinuation will be obtained and recorded on the CRF.

Replacement subjects may be added at SKLSI's discretion, in agreement with the investigator.

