Pharmacokinetic assessment for cenobamate in plasma

- $AUC_{\%extrap}$: Percentage of the AUC that was extrapolated
- C_{last} : Last quantifiable concentration
- $t_{1/2}$: Terminal half-life
- CL/F : Oral clearance
- λ_z : Terminal rate constant
- V_z/F : Apparent volume of distribution during terminal phase

Number of Subjects: 24

Subjects will be balanced amongst gender and ethnic groups to the extent possible. A subject who prematurely ends the study and who received treatment may be replaced. In case of discontinuation related to an adverse event, the replacement will be discussed between the Investigator and SKLSI.

Main Inclusion Criteria:

1. Male or female subjects of 18 to 50 years of age (inclusive), at the time of screening
2. Able to read, understand, sign, and date a written informed consent form (ICF) before study participation at screening
3. Agree to use effective methods of contraception as described in Section 12.1.7.8 and Section 12.1.7.9.
4. Body mass index (BMI) between 18.5 and 30.0 kg/m² (inclusive) at screening
5. Judged to be in good health on the basis of medical history, physical examination, and routine laboratory measurements (i.e., without clinically relevant pathology)
6. Electrocardiogram (ECG) (12-lead), arterial blood pressure, and heart rate within the normal range of the study center or considered not clinically significant by the Investigator.
7. Able to understand and comply with protocol requirements and instructions and likely to complete the study as planned
8. Females of non-childbearing potential (18 to 50 years of age (inclusive)), who have undergone a sterilization procedure at least 6 months prior to dosing with official documentation (e.g., bilateral tubal ligation or bilateral salpingectomy or hysterectomy), or be

postmenopausal with amenorrhea for at least 1 year prior to dosing and follicle-stimulating hormone (FSH) serum levels consistent with postmenopausal status as per Principal Investigator's judgment

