Treatment Administration			X																										
PK Blood Sampling			X	X	X	X	X	X	X	X	X	X	X	X	X	X	X	X	X	X	X	X	X	X	X				
Pharmacogenomic Blood Sampling		X																											
Discharge																				X									
Outpatient Visit																				X	X	X	X	X	X ⁱ	X			

Note: C-SSRS= Columbia Suicide Severity Rating Scale; AE = adverse event; BMI = body mass index; ECG = electrocardiogram; FSH = follicle stimulating hormone; h = hour; PK = pharmacokinetic

^a Review Inclusion/Exclusion on Day -1

^b Baseline “Baseline/Screening” version of C-SSRS will be used

^c “Since Last Visit” version of the C-SSRS will be used

^d Randomization to occur prior to dosing on Day 1.

^e Pregnancy testing for female subjects of childbearing potential only; postmenopausal women with last menses less than one year will have a serum pregnancy and FSH test during screening only

^f Postmenopausal women only, including women with last menses less than one year

^g Complete physical examination at Screening; Symptom-oriented physical examination on Day 1, Day 22, Day 43 and at follow-up

^h Vital signs (supine systolic and diastolic blood pressure, pulse rate, respiratory rate, and body temperature) measurement in supine position (at least 5 minutes).

ⁱ Note that Visit 17 only is an outpatient visit while Visit 7 and 12 are CRU admission days to bridge between periods

^j Visit 2 is baseline visit Visits 7 and 12 are the start of periods 2 and 3 respectively

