8. SELECTION AND WITHDRAWAL OF SUBJECTS

Healthy subjects who meet all the inclusion criteria and none of the exclusion criteria will be eligible for participation in this study. The study population will consist of a balanced representation of genders and ethnic groups to the extent possible.

Adherence to the study design requirements, including those specified in the schedule of assessments ([Table 4](#)), is essential and required for study conduct. Continued eligibility will be assessed upon entry into the clinic prior to the start of each visit.

All screening evaluations must be completed and reviewed to confirm that potential subjects meet all eligibility criteria. The subject's selected by the clinical site will be reviewed by SKLSI for final approval. The investigator will maintain a screening log in order to record details of all screened subjects and to confirm eligibility or record reasons for screening failure, as applicable.

Subjects may be re-screened only once within an appropriate time window in case of out of range results.

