8.1. Subject Inclusion Criteria

3. Male or female subjects of 18 to 50 years of age (inclusive), at the time of screening
4. Able to read, understand, sign, and date a written informed consent form (ICF) before study participation at screening
5. Agree to use effective methods of contraception as described in Section [12.1.7.8](#) and Section [12.1.7.9](#).
6. Body mass index (BMI) between 18.5 and 30.0 kg/m² (inclusive) at screening
7. Judged to be in good health on the basis of medical history, physical examination, and routine laboratory measurements (i.e., without clinically relevant pathology)
8. Electrocardiogram (ECG) (12-lead), arterial blood pressure, and heart rate within the normal range of the study center or considered not clinically significant by the Investigator.
9. Able to understand and comply with protocol requirements and instructions and likely to complete the study as planned
10. Females of non-childbearing potential (18 to 50 years of age (inclusive)), who have undergone a sterilization procedure at least 6 months prior to dosing with official documentation (e.g., bilateral tubal ligation or bilateral salpingectomy or hysterectomy), or be postmenopausal with amenorrhea for at least 1 year prior to dosing and follicle-stimulating hormone (FSH) serum levels consistent with postmenopausal status as per Principal Investigator's judgment

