9.2. Concomitant Medications

The use of any investigational drug is prohibited within 30 days before the first administration of cenobamate. The use of any prescription or over-the-counter drug (other than hormonal contraceptives for women of childbearing potential) is prohibited within less than 15 days before the first administration of cenobamate, with the exception of vitamin/mineral supplements and the occasional use of acetaminophen, which is allowed up to 24 hours before dosing in any treatment period.

For any subject, if the use of any concomitant treatment becomes necessary (e.g., for the treatment of an AE), the treatment must be recorded in the CRF, including the reason for treatment, generic name of the drug, dosage, route, and date and time of administration. If a treatment is administered, SKLSI's medical monitor must be promptly notified in order to assess the subject's eligibility for continuing study participation.

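### The protocol contradicts itself on whether women of childbearing potential may enrol; if they may, the mandatory pregnancy stop in 7.4.1 has no scheduled test behind it before doses 2 and 3

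*Protocol*

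**What the plan says.** **Eligibility.** Protocol section 8 says: "Healthy subjects who meet all the inclusion criteria and none of the exclusion criteria will be eligible for participation in this study". The only criterion in 8.1 specific to women is no. 10: "Females of non-childbearing potential (18 to 50 years of age (inclusive)), who have undergone a sterilization procedure", with confirmed postmenopausal status as the alternative. Synopsis criterion 8 is the same.

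Other sections provide for women outside that description:

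- Section 9.2 bars prior medication "other than hormonal contraceptives for women of childbearing potential", and 9.2.1 repeats the exemption.
- Section 12.1.8.8 defines women of childbearing potential and sets their contraception rules.
- Table 8 lists a serum pregnancy test for them.
- Table 4 footnote e reads: "Pregnancy testing for female subjects of childbearing potential only".

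**Stopping rule.** Section 7.4.1 lists the reasons for which a subject will be discontinued. One is "Females who are pregnant according to a positive pregnancy test"; another is a positive alcohol or drug screen.

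**Testing.** Table 4 and the visit lists schedule a serum pregnancy test at Screening and urine tests on Day -1 and Day 69. The Day 20 and Day 41 admissions (7.1.1.7, 7.1.1.12) list clinical labs, drug screen, breath alcohol, vital signs and C-SSRS, but no pregnancy test. SAP Table 2 shows the same schedule. SAP 6.2 places the pregnancy test under Screening only.

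**Action on a pregnancy.** Section 12.1.8.7 asks the investigator to discuss with the medical monitor or sponsor, together with the IRB, whether the subject should continue.

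**The concern.** A site reading 8.1 strictly would turn away any woman who could conceive. A site reading 9.2, 12.1.8.8 or footnote e would conclude that such women are expected, provided they use contraception. Both readings have support in the current text.

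Under the second reading, a pregnancy too early to show on Day -1, or begun while the woman was an outpatient in Period 1 or 2, could be followed by one or two further 200 mg doses. The stop depends on a positive test, and no test is scheduled in that interval. The Day 69 test can record such an exposure but cannot prevent it. What is at stake is avoidable fetal exposure in a healthy-volunteer study with no direct benefit to participants.

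The conflict between 7.4.1 and 12.1.8.7 is a separate matter: a site that does obtain a positive result has two different instructions.

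**Working it through.** **1. Which reading governs?** Section 8 requires every inclusion criterion to be met. Applied word for word, no. 10 would exclude men, so it has to be read as applying to women. The text does not say whether it restricts all women or describes one admissible subgroup. Against the restrictive reading stand 9.2, 9.2.1, 12.1.8.8, Table 8 and footnote e. Under the restrictive reading, the Day -1 and Day 69 urine tests have almost nobody to test.

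**2. Test days against dose days.** Inputs: doses on Days 1, 22 and 43 (synopsis); scheduled tests at Screening, Day -1 and Day 69 ± 1 (Table 4); no Day 0 (SAP 8.2), so Day -1 to Day 1 is one day.

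| Interval | Calculation | Days |
|---|---|---|
| Last test to dose 1 | Day -1 to Day 1 | 1 |
| Last test to dose 2 | 1 + (22 − 1) | 22 |
| Last test to dose 3 | 1 + (43 − 1) | 43 |
| Dose 3 to next test | 69 − 43 | 26 (25 to 27 with the window) |

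Scheduled tests after dose 1 and before dose 2: none. After dose 2 and before dose 3: none. By comparison, the alcohol and drug stop in the same 7.4.1 list is backed by screens at 120, 192, 264, 360 and 456 hours of each period.

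**3. Could another scheduled item fill the gap?** The clinical laboratory row in Table 4 does not, because serum and urine pregnancy tests have their own rows.

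**4. Scale.** The documents give no count of such women, no contraceptive failure rate and no detection lag, so these are assumptions.

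- Women affected: 0 under the strict reading. Upper bound: 24 / 2 = 12, if half the subjects are women and all could conceive.
- Exposure from Day -1 to dose 3: 12 × 43 / 365 = 1.41 woman-years.
- Expected pregnancies at an assumed 1% to 10% annual failure: 1.41 × 0.01 = 0.014 to 1.41 × 0.10 = 0.141.

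Sensitivity check: add 7 to 14 days before Day -1 for conceptions too early to detect then, and remove confinement days (Day -1 to 4 = 4; Day 20 to 25 = 5; Day 41 to 43 = 2; total 11), leaving 43 − 11 = 32.

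- 12 × (32 + 7) / 365 = 1.28 woman-years.
- 12 × (32 + 14) / 365 = 1.51 woman-years.
- Expected pregnancies: 1.28 × 0.01 = 0.013 to 1.51 × 0.10 = 0.151.

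The order of magnitude does not change.

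**The case against.** The best reply is that the condition may never be met. No. 10 limits women to documented sterilization or confirmed menopause, section 8 makes every criterion binding, and the amendment summary shows that this criterion was reworded with the limitation kept. On that reading no woman is affected and the defect is one of wording. This stands as a limit on the finding but does not dispose of it: the same amendment rewrote 9.2 and kept the exemption for women of childbearing potential.

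It is also fair that inclusion criterion 5 ("Agree to use effective methods of contraception as described in Section") proves little. It points to the male contraception section as well, and 12.1.8.8 counts tubal ligation as an acceptable method, so the criterion has work to do even if no woman who could conceive is enrolled.

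There are safeguards. The protocol says "Continued eligibility will be assessed upon entry into the clinic prior to the start of each visit". Section 12.1 lets the investigator add safety measurements, 7.4.1 allows withdrawal at any time for a significant safety risk, and 12.1.8.8 requires contraception and does not accept hormonal methods alone. These reduce the risk, but none is a scheduled pregnancy test. Contraception is also in force before dose 1, where the protocol still tests.

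A reader might infer that the protocol will dose pregnant women, or that the stop cannot operate at all. The documents support neither. Enrolment of such women is uncertain, and a positive result from any unscheduled test would still trigger 7.4.1.

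**Conclusion.** The eligibility contradiction and the conflict between 7.4.1 and 12.1.8.7 are present in the text and hold without assumptions. The testing gap is conditional: it matters only if women of childbearing potential may enrol. In that case no scheduled test can trigger the stop between Day -1 and Day 69, and doses 2 and 3 are given 22 and 43 days after the last one.

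Absolute risk is low: zero under the strict reading, and well below one expected pregnancy under the upper-bound assumptions. Those risk figures rest on inputs from outside the documents and show scale only. It would be wrong to infer any threat to the bioavailability or food-effect results; this is a matter of safety and conduct. It should be corrected because the two readings lead to different enrolment and the remedy is cheap.

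**What to change.** (a) State in 8.1 and in synopsis criterion 8 whether women of childbearing potential are eligible.

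(b) If they are not, remove or limit the provisions for them in 9.2, 9.2.1, 12.1.8.8, Table 8 and Table 4 footnote e.

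(c) If they are, add a urine pregnancy test for them at the Day 20 and Day 41 admissions (Table 4, 7.1.1.7, 7.1.1.12 and SAP Table 2), with the result read before the Day 22 and Day 43 doses. Correct SAP 6.2, which lists the pregnancy test under Screening only.

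(d) In either case, amend 12.1.8.7 so that a positive test means no further dose and the discussion concerns follow-up only.

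Cost: a short amendment touching several sections, with the IRB re-approval that 16.1 requires. Under (c) there are at most two extra urine tests per eligible woman (12 × 2 = 24 at the upper bound), at admissions where urine is already collected for the drug screen. No visit or blood draw is added. The downside is an occasional false positive that delays or removes a subject. A very recent conception could still be missed.
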